7.7 EXPOSURE TIME

Not applicable.

7.8 SAFETY ANALYSIS

Not applicable.

ANNEX 1. CODES FOR COMORBIDITIES AND OTHER COMEDICATIONS

Annex Table 1-1 ICD-10 codes for alcohol-related disorders

ICD-10 codes	Description
85.9 in ICD-10, and I85.00 in ICD-10-CM	Oesophageal varices without mention of bleeding
E24.4	Alcohol induced pseudo-Cushing's syndrome
F10.1-F10.9	Alcohol dependence syndrome/Mental and behavioural disorders due to use of alcohol: dependence syndrome
G31.2	Degeneration of nervous system due to alcohol
G62.1	Alcoholic polyneuropathy
G72.1	Alcoholic myopathy
I42.6	Alcoholic cardiomyopathy
I85.0 in ICD-10 and I85.01 in ICD-10 CM	Oesophageal varices with bleeding
I85.0 in ICD-10-CM	Oesophageal varices in diseases classified elsewhere/Secondary oesophageal varices with bleeding
K29.2	Alcoholic gastritis
K29.20	Alcoholic gastritis without mention of haemorrhage/Alcoholic gastritis
K29.21	Alcoholic gastritis with haemorrhage/Alcoholic gastritis
K70.x	Alcoholic liver disease
K85.2	Alcohol induced acute pancreatitis
K86.0	Alcohol induced chronic pancreatitis
Z50.2	Alcohol rehabilitation
Z71.4	Alcohol abuse counselling and surveillance
Z72.1	Alcohol use

Annex Table 1-2 ICPC codes for alcohol-related disorders

ICPC codes	Description
P15	Chronic alcohol abuse
P16	Acute alcohol abuse

Proprietary confidential information © 2017 Boehringer Ingelheim International GmbH or one or more of its affiliated companies

Annex Table 1-3 ICD-10 codes for overweight and obesity

ICD-10	Description
E66	Obesity
E68	Sequelae of hyperalimentation
Z68.25*	Body mass index (BMI) 25.0-25.9, adult
Z68.26*	Body mass index (BMI) 26.0-26.9, adult
Z68.27*	Body mass index (BMI) 27.0-27.9, adult
Z68.28*	Body mass index (BMI) 28.0-28.9, adult
Z68.29*	Body mass index (BMI) 29.0-29.9, adult
Z68.3*	Body mass index (BMI) 30-39, adult
Z68.4*	Body mass index (BMI) 40 or greater, adult

* To be used if coding is based on ICD-10-CM.

Annex Table 1-4 ICPC codes for overweight and obesity

ICPC	Description
T82	Obesity
T83	Overweight

Proprietary confidential information © 2017 Boehringer Ingelheim International GmbH or one or more of its affiliated companies

Annex Table 1-5 Other comorbidity

Disease description	ICD-10 code	ICPC code
Cardiovascular diseases	I00-I99	K73-K99
Ischaemic heart disease	I20-I25 or coronary reperfusion surgery and procedures	
Stable angina pectoris	I20.1, I20.8, I20.9	K74.02 Stable angina pectoris
Unstable angina pectoris	I20.0	K74.01 Unstable angina pectoris
Acute myocardial infarction	I21	K75 Acute myocardial infarction
Other acute or subacute ischaemic heart disease	I22-I24	K76 Ischaemic heart disease w/o angina
Chronic ischaemic heart disease	I25	No specific code
Coronary reperfusion surgery and procedures	List of codes to be developed according to each database dictionary	List of codes to be developed according to each database dictionary
Arrhythmias	I47-I49	K78-K80
Paroxysmal tachycardia	I47	K79 Paroxysmal tachycardia
Ventricular tachycardia	I47.0, I47.2	No specific code
Supraventricular tachycardia and unspecified	I47.1, I47.9	No specific code
Atrial fibrillation and flutter	I48	K78 Atrial fibrillation/flutter
Other cardiac arrhythmias	I49	K80 Ectopic beats all types
Ventricular fibrillation and flutter	I49.0	No specific code
Other cardiac arrhythmias	I49.1-I49.9	No specific code
Conduction disorders	I44-I45	K84 Heart disease other
Cardiac arrest	I46	No specific code
Heart failure	I50	K77 Heart failure
Cerebrovascular disease	I60-I69, G45	K89-K90
Cerebral haemorrhage (subarachnoid, intracerebral, other non-traumatic)	I60-I62	K89 Transient cerebral ischaemia
Cerebral infarction and stroke	I63, I64, G46.5	K90 Stroke/cerebrovascular accident
Transient ischaemic attack	G45	K89 Transient cerebral ischaemia
Other cerebrovascular disease and sequelae of cerebrovascular disease	I65-I69	No specific code

Proprietary confidential information © 2017 Boehringer Ingelheim International GmbH or one or more of its affiliated companies

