General practitioner outpatient diagnoses	Yes, in data subset PHARMO-GP ¹	No	Yes (a panel of 1,200 general practitioners) ²
Specialist diagnoses	Yes, those in the hospital (no outpatient hospital or non-hospital clinics) or as communicated to and recorded by the GP in PHARMO-GP (primary care)	Yes, those in the hospital (inpatient diagnosis) and hospital outpatient clinics (outpatient diagnosis) (not outside the hospital)	Yes (a panel of 40 pulmonologists) ³
Pharmacy-dispensed medications	Yes	Yes	No
Prescribed medications	Yes, in data subset PHARMO-GP ¹	No	Yes

GP = General Practitioner; IMS = IMS Health Information Solutions; PHARMO = PHARMO Database Network; RWE LPD = Real-World Evidence Longitudinal Patient Database.

- 1 For this study, data from the Out-patient Pharmacy Database and the Hospitalisation Database are available for the overall source population (approximately 4 million patients covered); the subcohort PHARMO-GP includes approximately 1 million patients with data in the Out-patient Pharmacy Database, the Hospitalisation Database, and the General Practitioner (GP) Database. The Out-patient Pharmacy Database will be used to identify medication use.
- 2 The GP panel covers a population of approximately 1.8 million active patients.
- 3 The pulmonologist panel covers a population of approximately 55,000 active patients.

The coding of diagnoses, procedures, and medications varies across databases ([Table 3](#)).

Proprietary confidential information © 2017 Boehringer Ingelheim International GmbH or one or more of its affiliated companies

Table 3 Types of diagnosis, procedures, and medication codes in the study databases

Type of code	PHARMO, The Netherlands	National Registers, Denmark	IMS RWE LPD, France
Diagnoses	Hospital: ICD-10 ¹ Primary health care: ICPC ²	ICD-10	Local in-house thesaurus that can be mapped to ICD-10
Procedures	CBV	NCSP version 1.16, 2012	Local in-house thesaurus that can be mapped to ICD-10
Medications	ATC	ATC	/ EphMRA mapped to ATC

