ATC = Anatomical Therapeutic Chemical; CBV = Centraal Beheer Verrichtingenbestand (codes), Dutch Hospital Data Foundation–owned registration system for procedures, which links to the Dutch Healthcare Authority (NZa) declaration codes and the Dutch Classification of Procedures; EphMRA = European Pharmaceutical Market Research Association; ICD-9 = *International Classification of Diseases, 9th Revision*; ICD-10 = *International Statistical Classification of Diseases and Related Health Problems, 10th Revision*; ICPC = International Classification of Primary Care; IMS = IMS Health Information Solutions; NCSP = *Nordic Medico-Statistical Committee's Classification of Surgical Procedures*; PHARMO = PHARMO Database Network; RWE LPD = Real-World Evidence Longitudinal Patient Database.

- 1 Hospital codes in PHARMO before 2011 were ICD-9 and CBV. PHARMO will work with ICD-9 codes and map them to ICD-10 codes before conducting the analysis.
- 2 Available for PHARMO-GP, a data subset of PHARMO with information from GPs.

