Annex Table 1-5 (cont'd) Other comorbidity

Disease description	ICD-10 code	ICPC code
Hypertension and hypertensive heart disease	I10-I15	K85 Elevated blood pressure (excl. K86-K87) K86 Hypertension without organ damage K87 Hypertension with organ damage
Diseases of arteries, arterioles, and capillaries	I70-I79, and peripheral arterial revascularisation procedures	K91 Atherosclerosis (excl. K76, K90) K92 Atherosclerosis/PVD
Peripheral arterial revascularisation procedures	List of codes to be developed according to each database dictionary	List of codes to be developed according to each database dictionary
Other form of heart diseases	I00-I09, I30-I43, I80-I99	K73 Congenital anomaly cardiovascular K81 Heart/arterial murmur NOS K82 Pulmonary heart disease K83 Heart valve disease NOS K94 Phlebitis/thrombophlebitis K95 Varicose veins of leg K96 Haemorrhoids K99 Cardiovascular disease other
Hyperlipidaemia	E78	T93 Lipid disorder
Diabetes mellitus	E10-E14	T90 Diabetes mellitus
Renal disease	N00-N39	U99 Urinary disease, other
Chronic kidney disease	N18	U99.01 Kidney insufficiency
Other renal disorders	N00-N17, N19, N25-N39	U99 (excl. U99.01)
Anaemias	D50-D64	B78-B83
Peptic ulcer disease	K25-K28	D85 Duodenal ulcer D86 Peptic ulcer other
Liver disease	K70-K77	D97 Liver disease NOS
Osteoporosis	M80-M82	L95 Osteoporosis
Rheumatoid arthritis and other inflammatory arthropathies	M05-M14	L88 Rheumatoid/seropositive arthritis
Systemic connective tissue diseases	M30-M36	No code

Proprietary confidential information © 2017 Boehringer Ingelheim International GmbH or one or more of its affiliated companies

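### In SAP Annex Table 1-5, three ICPC codes used for PHARMO-GP (K84, K76, K89) do not match the comorbidity rows they feed, and one residual row has a title narrower than its codes

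*SAP*

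**What the plan says.** SAP Annex Table 1-5 defines each comorbidity by an ICD-10 cell and an ICPC cell. SAP Section 7.2 names it as the code list for the comorbidity tables, which are produced for all new users, for adults, and for patients aged 40 or older with COPD.

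The entries at issue are:

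- *Conduction disorders*, I44-I45: ICPC "K84 Heart disease other".
- *Other acute or subacute ischaemic heart disease*, I22-I24: ICPC "K76 Ischaemic heart disease w/o angina". The next row, chronic ischaemic heart disease (I25), has no ICPC code.
- *Cerebral haemorrhage*, I60-I62: ICPC K89, labelled as transient cerebral ischaemia. The same code fills the transient ischaemic attack row (G45).
- *Other form of heart diseases*: ICD-10 "I00-I09, I30-I43, I80-I99". Its ICPC list includes "K95 Varicose veins of leg K96 Haemorrhoids" but not K84.

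SAP Table 3 limits ICPC to one source: "Available for PHARMO-GP, a data subset of PHARMO with information from GPs". Denmark is coded in ICD-10. France uses a "Local in-house thesaurus that can be mapped to ICD-10". Under SAP Section 5.3.5 a record at any time before or on the index date counts, and under Section 6.5 a patient with the code is taken to have the condition.

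**The concern.** Describing the baseline characteristics of new olodaterol users is one of the two primary objectives (Protocol Section 8; SAP Section 3). Under Section 6.5 no later step separates a loosely coded patient from a true case, so the annex cell is the definition.

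Three distortions follow in PHARMO-GP. Any residual GP heart diagnosis becomes a conduction disorder. GP-coded ischaemic disease that is not acute can be printed as acute or subacute, while the chronic row receives nothing from GP records. Every patient with a GP code for transient ischaemia is also shown with a history of cerebral haemorrhage. A reader comparing PHARMO-GP with Denmark or France could then see differences that come from the code list rather than from the patients.

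**Working it through.** The plan states no figure to reproduce, so the check compares each ICPC label with its row.

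| Row | ICD-10 | ICPC | Fit |
|---|---|---|---|
| Conduction disorders | I44-I45 | K84 | Residual label; does not name conduction disease |
| Other acute or subacute ischaemic | I22-I24 | K76 | Broader than the row; label does not say acute |
| Chronic ischaemic | I25 | none | No GP input |
| Cerebral haemorrhage | I60-I62 | K89 | Label names a different condition |
| Transient ischaemic attack | G45 | K89 | Fits |
| Other form of heart diseases | I00-I09, I30-I43, I80-I99 | K73, K81-K83, K94-K96, K99 | Codes fit the ICD-10 set; the title does not |

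**K84.** It appears in one specific row only, conduction disorders. It is absent from the residual heart row, where its label belongs. The table already has a convention for rows without a match: cardiac arrest, ventricular tachycardia and ventricular fibrillation all carry 'No specific code'. The convention was not applied here, so one row gains patients and another loses them.

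**K76.** It appears once. Its label separates it from angina but does not place it in time. The label of K91 in the same annex excludes K76 from atherosclerosis, which suggests that K76 holds some atherosclerotic heart disease. That is a hint, not proof. With no GP code for I25, a GP-coded patient with chronic disease can be counted only in the acute or subacute row.

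**K89.** It is the only ICPC code in both the haemorrhage row and the transient ischaemic attack row. The GP-coded count is therefore the same in both rows by construction.

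**Group totals.** The overall cardiovascular row takes K73-K99 and the cerebrovascular row takes K89-K90. Moving codes among their sub-rows leaves those two totals unchanged.

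**Reach.** SAP Table 2 gives about 4 million covered PHARMO patients, and "the subcohort PHARMO-GP includes approximately 1 million patients with data in the Out-patient Pharmacy Database". The share is 1/4 = 25%. ICPC contributes nothing in Denmark or France.

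**Illustration for K84, on assumed inputs only.** Let q be the share of PHARMO-GP users with K84 and s the share of those who truly have a conduction disorder. If none of the false positives has an I44-I45 record, the overstatement is q(1 - s). Take q = 5%:

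- s = 10%: 5 x 0.90 = 4.5 percentage points in PHARMO-GP; 4.5 x 0.25 = about 1.1 points over all PHARMO.
- s = 90%: 5 x 0.10 = 0.5 points; 0.5 x 0.25 = about 0.1 points over all PHARMO.

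The second figure in each line also assumes that 25% of PHARMO new users fall in the GP subset. The documents give neither q nor s.

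**The case against.** The strongest reply is that the consequences are small and may already be handled. The off-label outcome and COPD severity use none of these cardiac or cerebrovascular codes, and no confounding adjustment is planned. Analyses run separately by database, and within PHARMO-GP the same mapping applies to olodaterol and indacaterol. SAP Section 5.3.5 points to Section 9.2 for database-specific details. That section is not in the public text, and Section 5.3.3 shows free-text searches being used in PHARMO-GP for emphysema and COPD exacerbation. All of this stands. It limits the weight of the point but does not repair the annex rows, and nothing in the available text overrides them.

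A reader might also infer more than the documents support:

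- *That varicose veins and haemorrhoids are mis-mapped.* They are not. The row's ICD-10 set includes I80-I99, carried over unchanged from Protocol Annex Table 4:1, and the ICPC codes follow it. The fault is the title.
- *That the residual row is inflated by a known amount.* Assuming venous codes in 5-15% and other heart disease in 5-8%, independently, gives 1 - 0.95 x 0.95 = 9.8% to 1 - 0.85 x 0.92 = 21.8%. Every input is assumed, and the planned row is not restricted to the heart.
- *That every K76 patient is in the wrong row.* The label says neither acute nor chronic, so moving K76 wholesale to the chronic row would be equally unproven.
- *That "K85 Elevated blood pressure (excl. K86-K87") does not belong under hypertension.* Including it favours sensitivity. That is a choice, not an error.

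**Conclusion.** The point holds for three ICPC assignments and one row title. K84 is non-specific for conduction disorders, K76 is broader than acute or subacute ischaemic disease, and K89 names a condition other than cerebral haemorrhage. The mapping faults are confined to GP-coded diagnoses in the descriptive comorbidity tables of PHARMO-GP. The title problem applies to all three databases.

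The documents do not allow the error to be sized; the 0.5 to 4.5 points for K84 only illustrate the scale on assumed inputs. The conclusion rests on the labels as printed and on Section 9.2 not replacing these rows. It does not support a claim that the cardiovascular tables are wrong in general, or that the main result is at risk. The correction is worth making because a primary descriptive objective depends on the table and the change is cheap.

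**What to change.** Edit SAP Annex Table 1-5 before programming:

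1. *Conduction disorders*: set the ICPC cell to 'No specific code', report the row from I44-I45, and move K84 to the residual heart row.
2. *Ischaemic disease in PHARMO-GP*: report K76 in one combined I22-I25 row, titled ischaemic heart disease other than angina or acute myocardial infarction.
3. *Cerebral haemorrhage*: remove K89 and keep it under transient ischaemic attack.
4. *Other form of heart diseases*: rename it *Other heart and circulatory diseases* in all databases. The protocol's ICD-10 set stays as it is.
5. If Section 9.2 already overrides any of these rows, carry the override into the annex so that the two agree.

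No new data are needed. The price is fewer GP-derived positives for conduction disorders and cerebral haemorrhage, and a coarser split of ischaemic disease in PHARMO-GP.

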5.3.5 Other comorbidities

Characterisation of the patient population will include a description of the medical history of comorbidities listed in [Annex Table 1-5](#), which will be identified through recorded diagnosis at any time before or on the index date. Additional details on database-specific specifications are described in Section [9.2](#).

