7.2 CONCOMITANT DISEASES AND MEDICATION

Frequency of history of specific diseases and conditions of interest at any time before the index date will be assessed for each exposure group in each data source within the overall study population (Shell Table 5.1 and Shell Table 6.1). The same analysis will be repeated for adults (Shell Table 5.2 and Shell Table 6.2) and for those patients aged 40 years or older with a diagnosis of COPD (Shell Table 5.3 and Shell Table 6.3). Diagnosis of COPD, asthma, and other respiratory comorbidities and time since first COPD diagnosis will be included as part of the description of medical history. In this table, COPD, asthma, and respiratory comorbidities will not be mutually exclusive, and a patient will be allowed to be in more than one group. The comorbidities to be considered are listed in Sections [5.3.4](#) and [5.3.5](#), and a complete list of codes is included in [Annex Table 1-5](#).

The number and percentage of patients with a prescription or dispensing for a specific medication within the year before the index date will be described in each exposure group for the overall population (Shell Table 7.1 and Shell Table 8.1), for all adults (Shell Table 7.2 and Shell Table 8.2), and for those patients aged 40 years or older with a diagnosis of COPD (Shell Table 7.3 and Shell Table 8.3). A description of the medications considered is detailed in Section [5.3.6](#), and the list of codes is presented in [Annex Table 1-6](#).

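### SAP Annex Table 1-5 gives cerebral haemorrhage the ICPC code for transient ischaemia (K89), so unless SAP Section 9.2 overrides it, the PHARMO-GP haemorrhage row would count TIA patients

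*SAP*

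**What the plan says.** SAP Section 5.3.5 describes medical history using the conditions in Annex Table 1-5, "which will be identified through recorded diagnosis at any time before or on the index date". Section 7.2 says of the same annex that "a complete list of codes is included in" it. The annex is therefore the operative code list for this analysis, not background.

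In that table the row "Cerebral haemorrhage (subarachnoid, intracerebral, other non-traumatic" has ICD-10 I60-I62 and, in the ICPC column, "K89 Transient cerebral ischaemia". Two rows below, the transient ischaemic attack row (G45) has the same ICPC code and description.

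SAP Table 3 gives ICPC as the primary-care coding system in PHARMO, available for the PHARMO-GP subset. Denmark uses ICD-10, and the French source uses a thesaurus mapped to ICD-10.

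The annex is not the only place where definitions may sit. Section 5.3.5 adds: "Additional details on database-specific specifications are described in Section" 9.2. The opening of Section 5 is broader still and places in Section 9.2 the specifications that define the variables of interest in each data source. That section is not in the SAP text available to us.

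**The concern.** The SAP's own label for K89 is not haemorrhage, so the cell contradicts the row it stands in. No ICPC dictionary is needed to see this.

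SAP Sections 5.3 and 6.5 treat a recorded code as presence of the condition and the lack of one as absence. A wrong code therefore produces misclassification, not missing data, and nothing in the output would reveal it. If programmed as printed, the PHARMO-GP haemorrhage row would fail in both directions: it would take in patients coded for transient ischaemia and leave out haemorrhages that the GP coded differently.

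At stake is one line in the description of baseline characteristics. That description is a primary objective for olodaterol and a secondary one for indacaterol (SAP Section 3).

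**Working it through.** The plan gives no figure to reproduce, so the check is a comparison of code lists.

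**Step 1: the cerebrovascular rows side by side.** The inputs are protocol Annex Table 4:1 and SAP Annex Table 1-5.

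| Row | Protocol ICD-10 / ICD-9 | SAP ICD-10 | SAP ICPC |
|---|---|---|---|
| Cerebrovascular disease (parent) | I60-I69, G45 / 430-438 | I60-I69, G45 | K89-K90 |
| Cerebral haemorrhage | I60-I62 / 430-432 | I60-I62 | **K89** |
| Cerebral infarction and stroke | I63, I64, G46.5 / 433.1, 434.1, 436 | I63, I64, G46.5 | K90 |
| Transient ischaemic attack | G45 / 435 | G45 | **K89** |
| Other and sequelae | I65-I69 / 433.0, 434.0, 437, 438 | I65-I69 | marked as none |

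Haemorrhage and TIA share no code in the protocol or in the SAP's ICD-10 column. They merge only in the ICPC column, which the SAP added.

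**Step 2: is it a text-extraction fault?** Probably not. Code and description appear together in both rows, and the neighbouring entries line up: the range with the parent, K90 with stroke, and no code with the residual row.

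**Step 3: how the table treats poor matches elsewhere.** Seven rows are marked as having no specific ICPC code and one as having no code, 7 + 1 = 8 in all. Three subcodes are used: K74.02, "K74.01 Unstable angina pectoris" and "U99.01 Kidney insufficiency". The row for other renal disorders takes U99 with U99.01 excluded. K89 is the only ICPC code placed in two sibling rows without such an exclusion.

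**Step 4: what the printed cell does in PHARMO-GP.** Assume that a condition counts as present if either a hospital or a GP code is found. Let T be the patients with a GP-recorded K89, H those with hospital I60-I62, and G those with hospital G45. Then:

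- Haemorrhage row = H ∪ T
- TIA row = G ∪ T
- Haemorrhage count = |H| + |T| − |H ∩ T|, which is at least |T|

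Three things follow. From GP codes alone, the two rows are identical. With hospital codes added, the haemorrhage row can never be smaller than the GP K89 count. The patients who enter it through K89 alone number |T| − |H ∩ T|. The documents give none of these counts, so no number or percentage can be attached.

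**Step 5: reach.** The parent cerebrovascular row (K89-K90) and the cardiovascular row (K73-K99) contain both codes whichever sub-row they sit in, so they do not change. Denmark and France do not use the ICPC column. The code lists for COPD and asthma (SAP Table 5) and the COPD severity criteria (SAP Section 5.3.3) do not contain K89. SAP Section 7.4 has no confounding adjustment into which the row could feed.

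**The case against.** The strongest objection is that the consequence depends on text that cannot be seen. ICPC applies only to PHARMO-GP, and a PHARMO-specific definition in Section 9.2 is exactly where this cell would be confirmed or replaced. This stands. The duplicate entry is certain; a wrong haemorrhage count is conditional. A reader might infer that the haemorrhage results will be wrong, and the documents do not support that. If Section 9.2 does override the cell, however, the annex that Section 7.2 calls complete disagrees with it and still needs correcting.

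A second objection is that the ICPC column is an approximate crosswalk throughout. Conduction disorders carry the residual heart-disease code K84, renal disease carries U99, and the rheumatoid and other inflammatory arthropathies row has only L88. This also stands: it would be too strong to say that every other row either has an exact code or is marked as lacking one. Those rows, however, hold broad or partial codes. K89 in the haemorrhage row names a different condition that has its own row in the same table.

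A reader might also put a number on the affected results. Section 7.2 describes an overall analysis, then "The same analysis will be repeated for adults" and for patients aged 40 or older with COPD, which for two drugs suggests 3 × 2 = 6 estimates per report. That is not an upper bound. Section 7 further stratifies all analyses by LABA-naïve patients and switchers, and the table shells are in a separate file. No count of affected estimates can be defended.

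Finally, the matter is close to clerical, since no inference or classification uses the row. That is fair and sets the severity. It is still an operational code that a programmer would apply as written.

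**Conclusion.** The entry is wrong as written. Unless SAP Section 9.2 overrides it, every PHARMO-GP new user with a GP-recorded K89 would be counted as having cerebral haemorrhage. A haemorrhage under another GP code would be missed in that row unless a hospital code also exists.

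Severity is minor. The effect is limited to this descriptive sub-row for patients with GP data, in each population and stratum where it is tabulated. It would be tempting to extend the point to off-label prevalence or COPD severity, but neither definition uses K89.

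The conclusion rests on two assumptions: that the annex is programmed as printed, and that GP and hospital codes are combined by an either-or rule. Without the second, the GP-based part of the row would still consist only of K89 patients.

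**What to change.** 1. Remove K89 from the cerebral haemorrhage row and keep it for transient ischaemic attack only.
2. Check the PHARMO-GP code list for an ICPC subcode specific to haemorrhage, and enter it if there is one.
3. If there is none, mark the row as having no specific code, as the table does elsewhere. Identify haemorrhage in PHARMO from hospital I60-I62 codes, and state in the report that haemorrhages recorded only by the GP are not captured in that row.
4. Make Section 9.2 agree with the annex.

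The cost is one cell and two checks. No new data are needed, because PHARMO-GP patients also have Hospitalisation Database records (SAP Table 2, footnote 1), and pre-2011 ICD-9 hospital codes are to be mapped to ICD-10 (SAP Table 3, footnote 1).

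The downside arises only under step 3: GP-only haemorrhages drop out of the row. A labelled grouping with K90 for GP data would be an alternative, because the SAP labels that code as stroke or cerebrovascular accident. It would no longer separate haemorrhage from infarction, though, and the documents do not show how Dutch GPs code haemorrhage.
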